### **7.3.3 PET, MRI Biopsy:**

- Patients proceeding to surgery following PSMA PET and MRI may forgo biopsy.
- Patients not proceeding to surgery will undergo a SOC MRI-fusion biopsy based on the pre-biopsy scan detailed in 7.3.2. PET findings will be integrated into the planning of the fusion biopsy. See appendix C for details of the fusion biopsy.
- AE assessment: AEs will be assessed at the time of Ga-PSMA-11 administration and also at the appointment for biopsy (if done) any event not expected is collected including but not limited to: rash and shortness of breath.
- A sextant-based analysis will be performed. See appendix D for details of sextant analysis.
- A secondary “per lesion” analysis will also be performed.

- How the knowledge of the PSMA-PET informs treatment will be tracked. Examples of informing the decision include PSMA-PET detected additional intraprostatic cancer lesions diagnosed.

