## 7 STUDY PROCEDURES

### 7.1 Summary

This patient population will have low (**1** = Gleason 3 + 3) or intermediate risk (**2** = 3 + 4; **3** = 4 + 3) prostate cancer, or be at risk of having intermediate disease as evidenced by a 4K score  $\geq 20\%$ , or Select MDx  $\geq 20\%$ , or PSA Density  $\geq 0.15$ . Patients will be scheduled for a MRI as part of routine care for either surgical planning or for further biopsy. Following the informed consent process, patients who enroll in the study will receive a  $^{68}\text{Ga}$ -PSMA-11 PET study along with their standard of care (SOC) MRI on an PET-CT. If the Vision PET-CT is not available, a standard PET-CT and SOC MRI can be done with co-registration of PET and MRI done using software to generate the equivalent of the PET-CT images. Patients receiving SOC MRI guided biopsy will have the additional PET data factored into their guided biopsy plan. The sensitivity and specificity for lesion characterization will be evaluated, along with the ability of the tracer to inform the treatment planning. Patients receiving surgical removal of the prostate will have a slice-by-slice whole mount analysis to assess the sensitivity and specificity the PSMA PET.

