## 7.2 Study Calendar

	Screening/ Baseline (-180 days)	Biopsy if indicated	Imaging	Surgery if indicated
REQUIRED ASSESSMENTS				
Informed Consent	X			
Inclusion/Exclusion	X			
Medical History 	X			
PSMA dose and PET scan			X 	
SOC MRI				
SOC MRI-guided biopsy		X		
SOC PET-guided biopsy		X		
SOC Focal Therapy				X
Pathologic assessment of biopsy		X		
SOC prostatectomy				X
Pathologic assessment of whole mount				X

Footnotes:

1. Medical history may be obtained via medical records, as necessary.
2. A second  $^{68}\text{Ga}$ -PSMA-11 PET, approximately 6-12 months following initial scan may be requested, if: (1) the subject undergoes HIFU treatment and/or (2) during follow-up, is rescheduled for MRI-fusion biopsy as standard of care.

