designee, who will report the occurrence of any adverse events to the IRB.

- As in most clinical nuclear medicine procedures, these radiopharmaceuticals are administered at a sub-pharmacologic doses. Adverse events are exceedingly unlikely, as Ga-HBED-CC has been clinically employed, extensively and without reported incident, in clinical patient diagnostic imaging studies in prostate cancer patients in Germany and other European countries, as well as in over 100 patients locally.
- If there is a discrepancy between the PSMA and conventional MRI scan, the investigators will discuss the treatment plan with the patient at the investigator's discretion.
- If the patient does not undergo a prostatectomy, no further study procedures will be performed.
- If the Vision PET-CT is not available, a standard PET-CT and mpMRI may be done with software registration of PET and MR images.
- A patient may have a second Ga-PSMA-11 PET, approximately 6-12 months following initial scan, if: (1) the patient undergoes HIFU treatment and/or (2) during follow-up, is rescheduled for MRI-fusion biopsy as standard of care.

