## **11.4 OnCore Safety Reporting**

In addition to protocol- and regulatory-required safety reporting, all serious adverse events (SAEs) will be captured in the Oncore system within 1 business day of notification. Initial SAE reporting will include as much detail as available, with follow-up to provide complete information.

Attributions will be assessed to study drugs, procedures, study disease, and other alternate etiology.

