## 12.2 Adverse Event Reporting Requirements:

Adverse events will be recorded for the first study drug administration and also for the prostate biopsy (if indicated) regardless of whether or not the event(s) are considered related to trial medications. All AEs considered related to trial medication will be followed until resolution, return to baseline, or deemed clinically insignificant, even if this occurs post-trial.

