### **Fusion Biopsy Procedure**

Concurrent acquisition of  $^{68}\text{Ga}$ -PSMA-11 PET data will be added to our present standard-of-care prostate mpMRI protocol performed in support of surgery planning or fusion biopsy for patients with prostate cancer. There are commercially available devices which allow performing a biopsy by **fusing** the MR targeted lesion with the real-time trans-rectal ultrasound image and thereby increasing the chance of prostate cancer detection. The fusion biopsy will be performed in the urology clinic, with at least two cores from each regions-of-interest defined by both mpMRI and PET.

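### Biopsy adverse events are assessed only at the biopsy appointment, so delayed non-serious complications may go unrecorded although Section 12.2 undertakes to record biopsy events

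*Combined protocol and SAP*

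**What the plan says.** **Recording.** Section 12.2 covers the first tracer administration and "also for the prostate biopsy (if indicated) regardless of whether or not the event(s) are considered related to trial medications". It gives no window in days.

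**Timing and scope.** Sections 7.3.2 and 7.3.3 carry the same instruction. AEs are assessed when the tracer is given, and "also at the appointment for biopsy (if done) any event not expected is collected". The two examples named are rash and shortness of breath.

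**Follow-up.** Section 12.2 continues: "All AEs considered related to trial medication will be followed until resolution, return to baseline, or deemed clinically insignificant". It states no follow-up rule for AEs related to a procedure.

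**After the biopsy.** The Study Calendar (Section 7.2) has no AE row and no visit or call after biopsy. Section 7.3.2 says: "If the patient does not undergo a prostatectomy, no further study procedures will be performed".

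**What the study does to the biopsy.** Section 7.1 says: "Patients receiving SOC MRI guided biopsy will have the additional PET data factored into their guided biopsy plan". Section 7.3.3 integrates PET findings into fusion planning. Appendix C takes the biopsy "with at least two cores from each regions-of-interest defined by both mpMRI and PET". Appendix D re-assesses biopsy plans with all imaging known, to see whether intended sites change. Section 7.3.2 describes the scan as research, while the calendar lists "SOC PET-guided biopsy".

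**Serious events.** Section 11.4 says that "all serious adverse events (SAEs) will be captured in the Oncore system within 1 business day of notification", and lists procedures among the possible attributions.

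**The concern.** Section 12.2 makes a commitment that the visit instructions cannot deliver. An assessment at the biopsy appointment sees what happens before and during the procedure. It does not see what begins after the man has gone home, and nothing later in the plan looks for it.

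The study has its own reason to look. Beyond the tracer and the scan, any extra or redirected cores are a physical risk that the research adds to routine care. Section 9.4.2 counts additional lesions and sextants found as a secondary outcome of PET on the biopsy plan. The possible gain from PET-directed sampling is therefore measured by design, while delayed harm from the biopsy is not.

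**Working it through.** The plan gives no figure on this point, so the check sets the sections side by side.

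1. **When would a delayed biopsy event be found?** The scheduled assessments are at tracer administration and at the biopsy appointment (7.3.2, 7.3.3). The calendar offers no later contact. Section 7.3.4 lists no AE assessment at surgery. The sentence in 7.3.2 that ends study procedures for men without prostatectomy would, read literally, also exclude the biopsy check that the same section schedules. On either reading it supplies nothing after the biopsy. No scheduled point remains.

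2. **Which events are collected at the appointment?** Sections 7.3.2 and 7.3.3 restrict collection to events that are not expected. Section 12.2 has no such restriction.
   - In plain language, a known complication of biopsy is expected and could be left out.
   - Section 12.1.3 defines an unexpected event by its absence from the Investigator's Brochure or package insert. If those describe only the tracer, the same complication would count as unexpected and be collected.
   - The instruction can thus be read both ways, and only one reading agrees with 12.2.

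3. **What is followed to resolution?** Section 12.2 states a follow-up rule only where the AE is related to trial medication. A complication of a core is related to a procedure. It may be recorded, but no rule says how long it is then followed, unless it is serious.

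4. **What catches serious events?** Under Section 12.1.2 an inpatient admission is serious. Section 11.4 requires entry in OnCore within 1 business day, and Section 12.2.2 requires follow-up reports when new information arrives. The clock starts at notification, and no scheduled contact produces one.

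5. **Does the study add to the biopsy?** Sections 7.1 and 7.3.3 and Appendix D say that PET informs the plan and may alter sites. Appendix C is ambiguous. Its regions may be those seen on either modality or only those seen on both. On the first reading, each PET-only region adds at least 2 cores, so k such regions add at least 2 × k. On the second, PET-only regions carry no stated core count. The documents give no value for k.

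6. **How many men?** Section 2 says that the split between prostatectomy and surveillance need not be even, and Section 7.3.3 lets men going to surgery forgo biopsy. The number biopsied is not stated and cannot exceed the 36 enrolled.

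**The case against.** The strongest reply is that the safety net is wider than the visit instructions. Section 12.2 sets no end time for recording biopsy AEs and does not forbid following those unrelated to the tracer. Serious events have a capture route, attribution to procedures and follow-up reports (11.4, 12.1.2, 12.2.2). Section 11 requires weekly safety review, and Section 12.2.1 requires prompt reporting of unexpected, research-related problems that suggest greater risk. This stands, and it confines the gap to delayed non-serious events and to serious events of which the team never hears.

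A second reply also stands in part. Men not going to surgery have a standard fusion biopsy in any case, and the Figure 4 caption in Appendix D puts three biopsies in one session. A later bleed or infection could seldom be assigned to a PET-directed core. Better collection would describe the safety of the PET-informed biopsy as a whole; it would not isolate the harm of the added cores.

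Three stronger readings are tempting, and the documents do not support them:

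- A reader might infer that biopsy complications are all lost, or never followed once recorded. Events at the appointment are collected, serious ones have the route above, and 12.2 only omits a rule for the rest.
- A reader might infer that the standard-of-care label in the calendar pushes complications towards an unrelated attribution. Attribution is made to the investigational agent or intervention (12.1.4) and, for serious events, also to procedures (11.4). Nothing ties it to the label, which is an inconsistency to reconcile.
- A reader might want a probability that the trial misses an event. That needs an assumed complication rate and an assumed number biopsied, and it would cover complications of any core, including standard ones. It would not measure the risk that the study adds.

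**Conclusion.** The concern holds in limited form. Section 12.2 undertakes to record biopsy AEs, but the only stated assessment is at the appointment and is worded for events that are not expected. No later contact is planned, and follow-up to resolution is written only for tracer-related AEs. Delayed non-serious complications of a biopsy that the research PET can alter may go unrecorded. Serious ones are captured only on notification.

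No size can be put on this from the documents. The conclusion rests on two readings: that the calendar and Section 7.3 list every scheduled contact, and that PET findings can change or add to the targets, as Sections 7.1 and 7.3.3 and Appendix D indicate. It does not depend on how the Appendix C wording about regions is resolved. Sensitivity, specificity and ROC results are unaffected. The matter is safety ascertainment, and it should be corrected because the collection point as written comes before the delayed events it would need to catch.

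**What to change.** - **Add a check after the procedure.** In 7.3.2, 7.3.3 and 12.2, specify a biopsy AE assessment by chart review or at an existing routine contact, over a stated window that starts on the biopsy date. The 28-day period in 12.1.2 should not be borrowed. It concerns deaths after the last dose, and because no interval from scan to biopsy is fixed, it could close before the biopsy takes place.
- **Align the scope.** Collect all biopsy AEs in 7.3.2 and 7.3.3, so that they match 12.2.
- **Extend follow-up.** In 12.2, follow to resolution AEs related to study procedures, including PET-directed cores.
- **Record exposure.** Enter the number of PET-only cores per man, and clarify in Appendix C which regions the core count covers.
- **Reconcile the label.** Bring the calendar's PET-guided biopsy row into line with Sections 7.1 and 7.3.2, which treat the PET as additional, research data.

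The cost is protocol and case report form wording plus a chart check. The documents describe no routine contact after biopsy, so whether a new contact can be avoided depends on local practice; chart review avoids the question but sees only what reaches the record. More AEs will be recorded. Most will probably be due to the standard cores, and few can be assigned to a PET core.

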#### **7.3.4 Surgery and Pathology**

- The standard of care surgical procedure is performed as indicated by the cancer.
- Pathologic assessment: whole mount sections of prostate tissue and routine sections of lymph nodes if applicable will be fixed and analyzed by licensed pathologist per routine care. This typically happens within 2 weeks of prostatectomy.
- Additional study-related pathologic assessment: intraprostatic lesion-based assessment will be done to document the % Gleason pattern 3, 4, and 5 within each lesion.
- A sextant-based analysis will be performed. See appendix D for details of sextant analysis.
- A secondary “per lesion” analysis will also be performed.
- How the knowledge of the PSMA-PET informs treatment will be tracked. Examples of informing the decision include the number and location of Ga-PSMA-PET detected: additional intraprostatic cancer lesions diagnosed, extra-prostatic extension, seminal vesicle invasion, and lymph node invasion.
- Genomic studies (e.g. Decipher, mRNA sequencing, or similar) may be done as standard of care for medical management following biopsy or surgery or may be done for determining association of mRNA (e.g. FOLH1 or others) and imaging characteristics.

## **8 STUDY WITHDRAWAL/DISCONTINUATION**

Subjects must be discontinued from the study for the following reasons:

- Withdrawal of consent
- Investigator deems withdrawal necessary at any time if it is determined that it is not in the subjects best interest to continue, or if the subject is found to be noncompliant with study procedures.

If subject discontinues after administration of study drug, he or she will be encouraged to continue on study for safety procedures per protocol. Reason(s) for discontinuing must be clearly documented in the appropriate source documents.

## 9 STATISTICAL CONSIDERATIONS

### 9.1 Study Design

Prospective, phase 2 clinical trial, single arm

### 9.2 Study Population

The enrolled population comprises all patients who meet the eligibility criteria and are registered onto the study.

### 9.3 Sample Size

Table 1: Sample size calculation:

	sensitivity= 0.80	sensitivity= 0.85	sensitivity= 0.90	sensitivity= 0.95
Error allowed (d)= 7.5%	46	37	27	14
Error allowed (d)= 10%	27	21	15	8

Our sample size is based on the key primary endpoint of sensitivity to detect clinically significant (Gleason >6 and >5mm) cancer overall. In the Table above we summarized the sample size required to achieve a certain degree of accuracy for different sensitivity levels. All the calculations are based on the normal approximation of the binomial distribution. For this pilot, we will also assume the samples within each patient are independent statistically. Each patient has six samples for diagnostic testing (sextants) and the prevalence of cancer per sextant is estimated to be 40% (Eiber et al., 2016). The rows (d) present the marginal maximal error under 95% confidence interval and the columns represent the sensitivity rate. The numbers in Table 1 represent the required number of patients needed for each different combination of marginal error (d) and sensitivity rate. In other words, for a sensitivity of 90% and a marginal error of 7.5%, we

are 95% sure that the sensitivity lies between 82.5% and 97.5% if we enroll 27 patients. Based on Table 1, the maximal sample size is 46 assuming the sensitivity is 80%. Therefore, we decided 36 patients was adequate to ensure that the proposed trial can achieve certain accuracy of the sensitivity across the majority the scenarios considered in Table 1.

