Whole mount pathologic analysis of PET imaging in prostate cancer has been reported primarily out of Germany. No prospective trials were found combining PSMA, PET-CT, and whole-mount analysis. Furthermore, studies have focused on high-risk disease rather than low/intermediate risk. For example, a retrospective trial out of Germany (Eiber, et al. 2016) combined Ga-PSMA-11 and PET-CT and found improvement in Receiver operator curve (ROC) for PET-CT over MRI (0.73 to 0.88, p<0.001). Of the 53 patients, 53% were high risk. The authors concluded prospective studies were warranted for biopsy guidance. Recently, F-FACBC (Fluciclovine) was used with PET-CT and compared to MRI for biopsy guidance in a prospective clinical trial (Jambor, et al. 2017). F-FACBC had high sensitivity (87%), but low specificity (56%) resulting in a low ROC (0.72). F-FACBC is not specific for prostate cancer resulting in replacement with PSMA-based tracers in clinical practice.

[figure not shown]
The Urology-Radiology-Pathology team at Indiana University has been employing fusion biopsy since 2013 and has performed more than 600 during this time. A recent abstract presented at the annual meeting of the American Urologic Association in 2017 demonstrated 22% of index lesions (largest tumor) were missed by MRI ([name], et al. 2017), and MRI undersized the index cancer lesion when compared to final pathology (2.2cm vs. 1.9cm, p = 0.03). A tracer that is both more sensitive and specific is desired leading urologists to continue ultrasound template biopsies with MRI targeted biopsy.

The Ga-PSMA-11 (HBED-CC) radiopharmaceutical (Eder, et al. 2014; Eiber, et al. 2015, Afshar-Oromieh, et al. 2015) is structurally based on a class of urea-derived inhibitors of PSMA (Pillai, et al. 2016). The targeting peptide has been modified at its N-terminus to incorporate the HBED-CC chelating agent with an exceptionally high binding affinity (~1039) for the Ga3+ ion (Figure 1 and Table 1). Methods for on-demand

production of  $^{68}\text{Ga}$ -PSMA-11 are already established (IND # 131,806), based on our research use of this radiopharmaceutical in imaging patients with recurrent prostate cancer.

**Table 1.** PSMA Affinities of the PSMA-11 Agent Before, and After,  $\text{Ga}^{3+}$  Chelation

PSMA Ligand	IC50 (nM)
PSMA-11 HBED-CC	$5.7 \pm 0.5$
Ga-PSMA-11 HBED-CC	$6.1 \pm 0.8$

[figure not shown]

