## **5 ELIGIBILITY CRITERIA**

### **5.1 Inclusion Criteria**

To be considered eligible to participate in this study, a patient must meet all the inclusion criteria listed below:

1.  $\geq 18$  years of age
2. Must provide written informed consent

3. Presence of low or intermediate risk prostate cancer or at risk of having intermediate risk cancer
  - a. Intermediate risk prostate cancer:
    - i. Grade group **2** = 3 + 4, or
    - ii. Grade group **3** = 4 + 3
  - b. At Risk of intermediate risk prostate cancer:
    - i. 4K score  $\geq$  20%, or
    - ii. Select MDx  $\geq$  20%, or
    - iii. PSA Density  $\geq$  0.15
    - iv. Grade group 1= 3+3
- Note:** Where multiple cancer lesions are present on biopsy, it is allowable to have Gleason 8 or 9 cancer lesions if they are in addition to the intermediate risk cancer as described above.
4. Scheduled for MRI or has recently completed SOC MRI (within 6 months) for further biopsy, surgical removal, or focal therapy.
5. Willing and able to lie still for approximately 50 minutes in an enclosed space for the CT.

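### Does a 40% sextant prevalence borrowed from a higher-risk cohort, with sextants taken as independent, undermine the case for 36 patients?

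*Combined protocol and SAP*

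**What the plan says.** Section 9.3 bases the sample size on "sensitivity to detect clinically significant (Gleason >6 and >5mm) cancer overall". Table 1 lists the patients needed for four sensitivities (0.80 to 0.95) and two margins (7.5% and 10%), using the normal approximation at 95% confidence. Two further inputs convert sextants to patients. For the pilot, "we will also assume the samples within each patient are independent statistically"; and, with six sextants per man, "the prevalence of cancer per sextant is estimated to be 40" percent, cited to a 2016 study.

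From one cell of the table the section says that the investigators "are 95% sure that the sensitivity lies between 82.5% and 97.5% if we enroll 27 patients", for a sensitivity of 90%. It concludes that "36 patients was adequate to ensure that the proposed trial can achieve certain accuracy of the sensitivity across the majority the scenarios" in Table 1. It gives no margin at 36 patients.

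Section 3.1 says of earlier work: "Furthermore, studies have focused on high-risk disease rather than low/intermediate risk". Its example is the 2016 study: "Of the 53 patients, 53% were high risk". Section 5.1 admits men with "Presence of low or intermediate risk prostate cancer or at risk of having intermediate risk cancer". Section 9.7 plans GEE for sensitivity and specificity.

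**The concern.** Three things do not line up. The sized endpoint is clinically significant disease, but the 40% is described only as cancer, and Section 9.3 does not say which definition it uses. The 40% comes from a cohort that the protocol itself sets apart from its own population. And Appendix D treats 3+3 disease and lesions under 5 mm as generally not clinically relevant, so a man with only such lesions would usually add no positive sextant. There is no cap on low-risk or at-risk men, and Section 2 leaves the prostatectomy/surveillance split open.

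Independence is the second optimistic input. If detection is positively correlated within a man, the real interval will be wider than Table 1 implies.

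Table 1 varies sensitivity and margin but neither of these two inputs. At stake is the planned precision, which is the only justification given for 36 patients.

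**Working it through.** **Reproducing Table 1.** Positive sextants needed = 1.96² × s(1−s)/d². Patients = that number ÷ (6 × 0.40 = 2.4), rounded up.

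| Margin d | 0.80 | 0.85 | 0.90 | 0.95 |
|---|---|---|---|---|
| 7.5%: positives | 109.27 | 87.08 | 61.47 | 32.44 |
| 7.5%: patients (stated) | 46 (46) | 37 (37) | 26 (27) | 14 (14) |
| 10%: positives | 61.47 | 48.98 | 34.57 | 18.25 |
| 10%: patients (stated) | 26 (27) | 21 (21) | 15 (15) | 8 (8) |

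Six cells match. The two stated as 27 are one patient high (61.47/2.4 = 25.6), which is immaterial.

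**Margins at 36 patients.** There are 36 × 6 = 216 sextants. Effective positives = 216p/DE, where p is prevalence, DE = 1 + (m−1) × ICC, and the margin is 1.96 × √(s(1−s)/effective positives). The table uses the size-weighted m = 1 + 5p, which follows if the number of positive sextants per man is binomial. The documents give no other prevalence and no ICC, so every row after the first is an assumption.

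| Prevalence | ICC | Effective positives | Margin in points at 0.80 / 0.85 / 0.90 / 0.95 | Cells met of 8 |
|---|---|---|---|---|
| 40% | 0 | 86.4 | 8.4 / 7.5 / 6.3 / 4.6 | 6 |
| 40% | 0.1 | 72.0 | 9.2 / 8.2 / 6.9 / 5.0 | 6 |
| 40% | 0.3 | 54.0 | 10.7 / 9.5 / 8.0 / 5.8 | 4 |
| 35% | 0.1 | 64.3 | 9.8 / 8.7 / 7.3 / 5.3 | 6 |
| 30% | 0 | 64.8 | 9.7 / 8.7 / 7.3 / 5.3 | 6 |
| 30% | 0.1 | 56.3 | 10.4 / 9.3 / 7.8 / 5.7 | 4 |
| 20% | 0 | 43.2 | 11.9 / 10.6 / 8.9 / 6.5 | 3 |
| 20% | 0.3 | 33.2 | 13.6 / 12.1 / 10.2 / 7.4 | 2 |

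On the plan's inputs the two missed cells are 0.80 and 0.85 at 7.5%; the second is missed at 7.53 points.

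**Where the majority is lost.** Two cells (0.80 at 10% and 0.90 at 7.5%) share the requirement of 61.47 positives, so the count drops from 6 to 4 in one step.

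- Independence: 61.47/216 = 28.5% prevalence.
- 40% prevalence: DE = 86.4/61.47 = 1.406. The ICC limit is 0.406/2 = 0.20 with size-weighted m = 3.0, or 0.406/1.4 = 0.29 with fixed m = 6p = 2.4.
- 30% prevalence: DE = 64.8/61.47 = 1.054. The ICC limit is 0.054/1.5 = 0.04 or 0.054/0.8 = 0.07.

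If cancer burden varies strongly between men, m is larger and these ICC limits are lower. At the extreme of m = 6 the limit at 40% would be 0.406/5 = 0.08.

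**The worked example.** 27 patients give 27 × 2.4 = 64.8 positives and a margin of 1.96 × √(0.09/64.8) = 7.3 points. It passes 7.5 points below 61.47/162 = 37.9% prevalence, and reaches 8.4 at 30% and 10.3 at 20%. A cell that is only just met is tight by construction, so this fragility is not an error.

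**The case for a change.** The best case for a change is that precision is all that supports 36 patients, and the two sentences reporting it carry no condition of their own. The pilot caveat in Section 9.3 is attached to independence and not to prevalence, and the hypothesis-generating remark in Section 9.7 is attached to the PET–MRI comparison. Modest departures in both inputs together (30% with ICC 0.1) already lose the majority. Stating the definition behind the 40%, with a small range of margins, would cost a few lines and would help whoever plans the larger study.

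Much of that is true. The definition is unstated, and a lower prevalence of significant disease in this population is a reasonable inference. It is still only an inference. The 40% may already apply a significance threshold; 47% of the source cohort were not high risk; some men may be upgraded at pathology; and Section 5.1 allows Gleason 8 or 9 lesions in addition to intermediate-risk cancer. Appendix D also takes its sextant method from the same 2016 study, so using that study's prevalence has a documented basis. The missing conditions are not hidden either: both assumptions stand in the same paragraph, ahead of the sentences that depend on them, and the final claim is limited to the Table 1 scenarios. An added range would rest wholly on assumed values.

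**Conclusion.** No change follows. This is missing detail around a declared pilot simplification. Section 9.3 is right on its own inputs, and its claim for 36 patients is modest: some degree of accuracy in most of the scenarios listed, which is 6 of 8. If prevalence were as low as 20% with independent sextants, the margins would be about 2 to 3.5 points wider (6.3 to 8.9 at sensitivity 0.90) and 3 of 8 cells would be met. That figure rests on an assumed prevalence, as every alternative scenario must here.

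Nothing the trial does or concludes depends on the planning margin. No decision rule is tied to it, and the number of patients and the endpoint stay as they are. GEE with its usual cluster-robust variance will give an interval that reflects the positive sextants observed and their correlation, so a shortfall in precision would show in the reported result. The authors could name the definition behind the 40% and the risk mix of its source when they next edit Section 9.3, but that is optional.
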